4.2 Number of Participants

Formative Work: We will conduct six focus groups with a total of 30 participants (10 high-school aged adolescents [aged 16-19], 10 college-aged youth {aged 18-22}, and 10 adult school-based behavioral health providers [aged 18-80]) during development. We will conduct approximately 10 interviews with adults who report misuse of substances in their youth. We will conduct approximately 6 play-testing focus groups with input from adolescents and/or college-aged youth each (n=10-20), high school youth aged 16-22, and focus groups of school-based mental health providers and/or providers who specialize in addiction who are aged 18-80 (n=10-20) to iteratively improve and finalize the game.

Pilot Study: The study will enroll 60 high-school-aged adolescents (aged 13-19) (n=60).

4.3 Selection Criteria

Formative Work:

High-school aged adolescent participants must: 1) attend a high school; 2) be aged 16-19; 3) English-speaking; 4) be willing to engage in discussions around mental health (e.g., potential warning signs, coping strategies, and help-seeking behaviors) related to suicide prevention and opioid misuse; and 5) if attending via Zoom, have access to Internet and a device for Zoom.

College-aged participants must: 1) attend a college/university; 2) be aged 18-22; 3) English-speaking; 4) be willing to engage in discussions around mental health (e.g., potential warning signs, coping strategies, and help-seeking behaviors) related to suicide prevention

and opioid misuse; and 5) if attending via Zoom, have access to Internet and a device for Zoom.

Adult school-based behavioral health provider and/or providers with expertise in addiction medicine participants must: 1) provide behavioral health services in a high school (if school-based) or provide addiction medicine services (if expertise in addiction medicine), 2) be aged 18-80, 3) English-speaking, 4) be willing to engage in discussions around mental health (e.g., potential warning signs, coping strategies, and help-seeking behaviors) related to suicide prevention and opioid misuse; and 5) if attending via Zoom, have access to Internet and a device for Zoom.

Pilot Study:

Inclusion criteria: For the pilot study, participants must: 1) attend a high school that has a school-based provider; 2) be between the ages of 13-19; 3) fluent in reading English during the consent process; 4) be willing to sit for a single session to complete pre-/post-assessments, engage with the game (~45min), and participate in a post-gameplay focus group (if in the experimental group) for 60min; and 5) provide assent and parental/guardian consent (if<age 18).

Exclusion criteria: Any student who is actively suicidal and/or moderately severe to severely depressed will not be eligible and will be immediately referred to the school-based provider on site to who will follow school protocol (e.g., contact 211, notify parent/guardian, and/or contact their local emergency department, etc.), as needed. Student may return to rescreen for participation according to the criteria on page 16.

Rescreening: Participants will not have to repeat the questions related to static variables (such as demographics and past experiences), but the baseline assessment of dynamic variables will need to be repeated and meet eligibility requirements .

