Aim 2: Evaluation Activities (Year 2): In collaboration with CT and MDCP schools, where we have partnerships, we will conduct a pilot study with 60 adolescents (aged 13-19). We will examine usability and acceptability of the gameplay experience, and feasibility of delivering the game and piloting protocols in schools. We will also explore proximal outcomes as potential means for behavior change in supportED vs. control group at 3 months on: 1) intentions to use safety plan; 2) coping strategies; and, 3) suicidal thoughts and associated risk factors (e.g., pessimism, helplessness, limited social support, and despair).

Completion of these aims will generate an evidence-informed, novel approach to addressing the intersection of suicide and prescription opioid/substance misuse among adolescents and, ideally, reduce the risk of suicide among a population who may experience greater risk

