We will collect participant demographic data including self-reported sex at birth, gender identity, sexual orientation, race, and ethnicity to determine subgroup similarities and/or differences. We will collect assessment data before and immediately after the participants engage with the game as well as at 3 months following gameplay. The primary outcomes of the proposed study are to examine: 1) the usability (e.g., ease of use) and acceptability (e.g., gameplay satisfaction) of the game among adolescents; and 2) the feasibility of delivering the game and piloting protocols in schools. To assess usability, acceptability, and feasibility, directly following supportED game completion, we will collect focus group data on participants' experiences. The following proximal outcomes, as mechanisms for behavior change, will be measured: 1) intentions to use safety plan;^r 2) coping strategies through adaptive and maladaptive subscales;^s and 3) severity of suicidal thoughts and associated risk factors using the Concise Health Risk Tracking Self-Report (CHRT-SR) comprised of the following subscales: Propensity (including domains of Pessimism, Helplessness, Limited Social Support, and Despair), Impulsivity, and Suicidal Thoughts.^t We will measure substance misuse in past 30^u days as a possible mediator. These scales will be self-reported by adolescents.

All of our data will be self-reported data; therefore, we will use data collection methods such as confidential self-administration that have been effective in our trials to minimize social desirability bias in self-reported data. Participants will receive \$25 gift cards as compensation for completion of assessments at each timepoint (e.g., baseline/post-game and 3-month follow up)

The Yale University Human Subjects Committee (the committee that reviews, approves, and monitors research on human subjects) may inspect study records. All published results will be group data. Information that will be collected during the focus group interviews will be erased 24 months after the completion of the study and after review of their content has been completed.

- 1. Formative and development work: (1 year)**

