 2. We will work iteratively with our target audience of 16-19-year old adolescents within schools, college-aged youth for a reflection of that age range, and school-based mental health providers to develop videogame content, collecting qualitative data for the videogame and refining our logic model with input from 4 focus groups of 5 high school-/college-aged youth each (n=20), aged 16-19 and 2 focus groups of 5 school-based mental health providers aged 18-80 (n=10).
 3. We will create the “Game Playbook” specific to this new digital game. Game Playbooks are our game manuals. We create behavior change gameplay manuals to accommodate the specific needs of a multi-disciplinary game development team. The playbooks outline the theoretical foundations and gameplay elements. This ensures targeted theoretical principles and behavior change mechanisms and constructs are included in the videogame.
 4. We will build the new digital game by creating new content, developed from focus groups and from the suicide and opioid misuse prevention literature, for our game development team, DigitalMill, Inc.
 5. We will conduct play-testing focus groups with input from focus groups of 5 high school-/college-aged youth each (n=20), aged 13-19 and focus groups with adults who specialize in addiction medicine 18-80 (n=10) to assess user experience (e.g., acceptability and usability) and feasibility of protocol to prepare for a larger pilot study that will require a new protocol (N=60).
- 6. Pilot Study:**
 7. We will conduct a pilot study with (N=60) adolescents between the ages of 13-19. We will examine the usability and acceptability of the game among adolescents, and the feasibility in conducting the study in schools.
Inclusion criteria: For the pilot study, participants must: 1) attend a high school that has a school-based behavioral provider; 2) be between the ages of 13-19; 3) be

fluent in reading English as determined in consent process; 4) be willing to sit for a single session to complete pre-/post-assessments, engage with the game (~45min), and participate in a post-gameplay focus group (if in the experimental group) for 60min; and 5) provide assent and parental/guardian consent (if < age 18).

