8. We will also assess proximal outcomes as potential means for behavior change in supportED vs. control group at 3 months. Examples include but are not limited to: 1) intentions to use safety plan; 2) coping strategies; and, 3) suicidal thoughts and associated risk factors (e.g., pessimism, helplessness, limited social support, and despair).

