DATA COLLECTED: We will collect name of student and parent/guardian if under 18, their email addresses and phone numbers to obtain assents/consents. This information will be de-identified prior to the start of research. We will collect participant demographic data including self-reported sex at birth, gender identity, sexual orientation, race, and ethnicity to determine subgroup similarities and/or differences. We will collect assessment data before and immediately after the participants engage with the game as well as at 3 months following gameplay. The primary outcomes of the proposed study are to examine: 1) the usability (e.g., ease of use) and acceptability (e.g., gameplay satisfaction) of the game among adolescents; and 2) the feasibility of delivering the protocols and procedures of conducting the study in schools. To assess usability, acceptability, and feasibility, directly following supportED game completion, we will collect focus group data on participants' experiences. The following proximal outcomes, as mechanisms for behavior change, will be measured including but not limited to: 1) intentions to use safety plan;⁷⁴ 2) coping strategies through adaptive and maladaptive subscales;⁷⁵ and 3) severity of suicidal thoughts and associated risk factors using the Concise Health Risk Tracking Self-Report (CHRT-SR) comprised of the following subscales: Propensity (including domains of Pessimism, Helplessness, Limited Social Support, and Despair), Impulsivity, and Suicidal Thoughts. We will measure substance misuse in past 30 days as a possible mediator. These scales will be self-reported by adolescents. Participants will receive \$25 gift cards as compensation for completion of assessments at each timepoint (e.g., baseline/post-game and 3-month follow up).

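### Pilot inclusion criterion 4 asks for willingness to attend one session only, although the exploratory between-arm comparison is at 3 months

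*Combined protocol and SAP*

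**What the plan says.** Section 4.3 (Pilot Study) requires participants to "be willing to sit for a single session to complete pre-/post-assessments, engage with the game (~45min), and participate in a post-gameplay focus group", the last element applying to the experimental group. Section 6.1 repeats the criterion in almost the same words: "be willing to sit for a single session to complete pre-/post-assessments". Neither list refers to a later visit.

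The between-arm question is set at a later visit. Aim 2 in section 2.1 has two parts. The first is "We will examine usability and acceptability of the gameplay experience, and feasibility of delivering the game and piloting protocols in schools". The second is to "explore proximal outcomes as potential means for behavior change in supportED vs. control group at 3 months". Section 6.1 says the same: "We will also assess proximal outcomes as potential means for behavior change in supportED vs. control group at 3 months". Assessments are taken before gameplay, then "immediately after the participants engage with the game as well as at 3 months following gameplay". The mixed model in section 7.2 uses all three time points. Section 6.8 schedules Brief COPE, the coping measure, at baseline and 3 months only.

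The primary outcomes in section 6.1 are usability, acceptability and feasibility, for which "directly following supportED game completion, we will collect focus group data".

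The 3-month visit is provided for elsewhere. A gift card is paid for it (4.4, 6.1, 6.4), and a school-based provider is on site for it (6.4). No retention target, dropout allowance, tracing procedure or missing-data method is given for the pilot.

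On contact details, section 6.4 says that names, email addresses and phone numbers are collected to obtain assent and consent, and then: "This information will be de-identified prior to the start of research". Section 8.3 keeps a separate master file linking names and telephone numbers to study IDs.

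**The concern.** The eligibility rule does not match the visit schedule. A student who is content to attend once but has no intention of returning satisfies criterion 4 as written and can be randomised. Each such student takes up one of 60 places and supplies no 3-month value. With 30 per arm, a few of them visibly widen the interval around the 3-month difference. If the likelihood of returning differs between a student who played the study game and joined a focus group and one who played an unrelated game, the contrast may also be biased. Some later dropout cannot be avoided, but enrolling students already known to be unwilling to return can be.

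**Working it through.** **1. Which data depend on the 3-month visit**

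- Usability, acceptability and feasibility (primary; 6.1, 6.4, 6.8): collected around the gameplay session. They do not depend on return. The focus group is held in the supportED arm only, so what a student contributes here depends on arm, but not on the later visit.
- Proximal outcomes at baseline and post-game (6.1, 7.2): collected at the session. They do not depend on return.
- Proximal outcomes at 3 months, supportED vs control (2.1, 6.1, 7.2): depend wholly on return.
- Change in Brief COPE (6.8): the schedule names baseline and 3 months and no post-game value, so a non-returner has no change score at all.

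A non-returner is therefore missing from the 3-month contrast and, for coping, from any measure of change. A likelihood-based mixed model would keep the student's earlier data, but it cannot supply the missing 3-month value. It would rely on a missing-at-random assumption that section 7.2 does not state.

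**2. What loss of 3-month data does to precision**

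There is no figure of the plan's own to reproduce. Section 7.1 gives N = 60 with no effect size, SD, power or dropout allowance, and section 5.1 says the study is not powered for efficacy.

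Inputs from the documents: 30 per arm, 1:1 (5.3); significance threshold 0.05 (7.2). Assumptions made here: two-sided test, 80% power, a simple two-sample t-test on 3-month completers, and equal loss in both arms of 0 to 30% from any cause.

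Completers per arm: n = 30 × (1 − loss), giving 30, 27, 24 and 21.

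The detectable difference d, in SD units, solves P(|T| > t(0.975; 2n − 2)) = 0.80, where T is noncentral t with 2n − 2 degrees of freedom and noncentrality d × √(n/2). As a check, the normal approximation is d ≈ (1.960 + 0.842) × √(2/n); for n = 30 this is 2.802 × 0.2582 = 0.723. The 95% interval half-width is 1.96 × √(2/n).

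| Assumed loss | n per arm | d, noncentral t | d, normal approx. | 95% CI half-width (SD) |
|---|---|---|---|---|
| 0% | 30 | 0.736 | 0.723 | 0.51 |
| 10% | 27 | 0.777 | 0.762 | 0.53 |
| 20% | 24 | 0.826 | 0.809 | 0.57 |
| 30% | 21 | 0.886 | 0.865 | 0.61 |

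These figures ignore baseline adjustment, repeated measures and clustering by school. They describe attrition from any cause. Nothing in the documents says how much of it would come from the wording of criterion 4.

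**3. Contact details**

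Read literally, section 6.4 gives obtaining consent as the only purpose of the contact details and removes identifiers before the research begins, which leaves no stated route to a student at 3 months. Section 8.3 supplies that route through the master file. The two can be squared if the wording in 6.4 means coding by study ID, but the text does not say so.

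**The case against.** A reader might infer that students who do not return are lost from Aim 2. The documents do not support that. The first part of Aim 2, which carries the primary outcomes, is served at the session, and baseline and post-game values still enter the mixed model. Only the 3-month contrast loses them.

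It can also be said that criterion 4 merely describes what happens in one sitting, and that the commitment to return may lie in the consent and assent that criterion 5 requires. Those pages are not available for review, so this cannot be excluded. The gift card and the on-site provider show that the visit is intended. These points stand, and they limit the claim to what the criteria say. They also make the omission look like an oversight, since nothing suggests that the visit was meant to be optional.

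The strongest objection is that a check made before randomisation cannot prevent dropout caused by the allocated game, and that students may withdraw at any point (6.5). This is correct. The added clause removes students who never meant to return; it does nothing about arm-related loss that arises afterwards. It is also fair that the SD figures do not measure the effect of this wording.

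Finally, a reader might take section 6.4 to mean that re-contact is impossible. The master file in section 8.3 answers that, and only a wording conflict is left.

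**Conclusion.** The point holds as a mismatch between eligibility and visit schedule: criterion 4 names one session in both lists, while the between-arm comparison, and all of the coping change data, need a second visit. The consequence is avoidable loss of 3-month data, with lower precision and a possible, undocumented, attrition bias. It does not threaten a primary objective, because the affected comparison is exploratory (7.2) and expressly unpowered (5.1).

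The size of the loss is unknown. If total loss were 20%, the detectable difference would move from about 0.74 to 0.83 SD, and at 30% to about 0.89 SD. This rests on the assumed loss rates, a two-sided 5% test, 80% power and a completers-only comparison. The change is worth making because it is cheap and the study is small. Whether the consent form already covers the 3-month visit could not be checked.

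**What to change.** In sections 4.3 and 6.1, extend pilot criterion 4 to add willingness to complete the 3-month follow-up assessment, and confirm it with the student before randomisation. This costs one clause in each section, matching consent and assent wording if it is not already there, and no additional visit. The downside is that a few students willing to attend only once are not enrolled, so the acceptability findings come from slightly more committed volunteers. The clause does not replace a statement of expected retention and of how missing 3-month data will be handled, which section 7 lacks.

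As a minor wording change, reconcile section 6.4 with section 8.3: say that research data are coded by study ID and that contact details stay in the separate master file until the 3-month assessment is done.

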5.7 Restrictions

Participants will engage with the device for a restricted period of 45 minutes (one-time session).

6 - Study Design

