Our research team will be trained by [name] team and the Pitt Methods workshop prior to commencing the study in all procedures, risk and protection methods, and safety related to conducting suicide **prevention** research. Eligible individuals will be assigned to either the 1) supportED group (n=30) or 2) control group (n=30). Both groups will also receive NIDA/NIMH pamphlets on substance misuse and mental health for youth at the end of the session. Prior to receiving pamphlets, those in the supportED group will engage with the game for one session (~45min) while the control group will engage with a non-health-related game for the same duration. Given schools do not have a standardized approach to address suicide prevention, we opted to use an attention/time control condition.

Participants will use a dedicated device (e.g., tablet) to access their digital experience on the web. The research staff with [name] always there will be present to monitor gameplay, to provide support, if needed, and to field questions in person. A school-based provider will be present for direct referrals, as needed. The total duration and number of sessions is consistent with those found in safety planning and with the amount adolescents engaged with our empowerED game.^q To pilot the feasibility of protocols, we will collect proximal outcomes, as possible mechanisms for behavior change. Proximal outcomes include but are not limited to the following measures: 1) intention to use safety planning; 2) coping strategies; and 3) severity of suicidal thoughts and associated risk factors (e.g., pessimism, helplessness, limited social support, and despair). We will also measure severity of suicidal ideation and attempts

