6.4 Study Procedures

Formative Work: Participants will engage in six 60-90-minute focus groups led by a licensed professional counselor, and a co-facilitator who will observe and take notes. Focus groups will be audio-recorded and held in a private room within the school if conducted in a school or held via Zoom if conducted virtually. Participants will be asked questions developed from a semi-structured focus group guide, which will first be pilot tested. Questions will be grounded in constructs of a safety planning intervention^w as well as self-determination^w and social cognitive theories^x and techniques used in Motivational Interviewing.^y Participants will

be asked to not share any identifiable information. Should any be shared, it will be redacted from transcripts. Participants will receive a \$25 gift card to participate. Same procedures will be in place for play-testing focus groups.

Pilot Study: We will pilot test *supportED* to examine usability, acceptability, and feasibility. We will enroll 60 adolescents who attend one of our partner school sites. To determine feasibility in piloting protocols, we will also explore proximal outcomes. Eligible individuals will be assigned to either the 1) supportED group (n=30) or 2) control group (n=30). Both groups will also receive NIDA/NIMH pamphlets on substance misuse for youth at the end of the session. Prior to receiving pamphlets, those in the supportED group will engage with the game for one session (~45min) while the control group will engage with a non-health related game for the same duration. Given schools do not have a standardized approach to address suicide prevention, we opted to use an attention/time control condition. Participants will use a dedicated device (e.g., tablet) to access their digital experience on the web. The research staff with [name] always there will be present to monitor gameplay, to provide support, if needed, and to field questions in person. A school-based provider will be present for immediate referrals, as needed.

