The total session lasting approximately 90 minutes. The facilitator will ask adolescents to sign assent form and provide clarification or answer any questions about the study procedure. Prior to the session, we will share flyers with educators, school-based providers, and our youth advisory board who will share with participants. Students may then share with other students (e.g., snowball sampling). The flyers contain a QR code for students to input their first/last name, phone number, and email address. If they are younger than 18, they must input parent/guardian first and last name, phone number, and email address.

Research staff will then contact them to obtain consent/e-consent. When needed, study staff will be available to parents/guardians should they have any questions. Before students are able to participate in the research study, they must have a signed assent and parent/guardian consent if under 18.

When the gameplay portion of the session begins, participants will play the game on an iPad or desktop device. A member of the research team or the facilitator will be there to provide assistance at all times. After completing the game, adolescents will be asked to participate in a questionnaire session and focus group about their overall gameplay experience. This will be facilitated by one of the members of the research team. The responses of the participants will be gathered and documented as data, which will be kept confidential. If at any point a student is flagged as moderate to high risk due to concerns related to substance misuse, depression, and/or suicide, they will be immediately referred to the school-based provider who will be on site during baseline and 3-month follow up. If a student is triggered by the sensitive nature of the topics, their school-based provider will be able to provide emotional support and/or referral to services. These same procedures will be utilized in local CT schools and in Miami-Dade County public schools.

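### The post-game focus group is planned for the supportED arm only, so the exploratory 3-month contrast is supportED plus focus group versus control game, and play plus group does not fit the stated 90-minute session

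*Combined protocol and SAP*

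**What the plan says.** **Who attends the group.** Section 4.3 (Pilot Study) asks participants to "be willing to sit for a single session to complete pre-/post-assessments, engage with the game (~45min") and to "participate in a post-gameplay focus group (if in the experimental group) for 60min". Section 6.1 (pilot item 7) repeats this criterion almost word for word. The data-collection text in 6.4 ties the group to the same arm: "directly following supportED game completion, we will collect focus group data". Section 6.1 says the same. Section 6.8 describes the group as covering both the content of the game and the way it is presented.

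**What the control receives.** Section 6.1 gives the reasoning: "Given schools do not have a standardized approach to address suicide prevention, we opted to use an attention/time control condition". Section 6.4 states what is matched: "the control group will engage with a non-health related game for the same duration". The Synopsis and Section 5.2 say the same.

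**When outcomes are measured.** Section 6.1: "We will collect assessment data before and immediately after the participants engage with the game as well as at 3 months following gameplay". Section 6.1 (item 8) compares the arms on proximal outcomes at 3 months. Section 7.2 fits a mixed model to baseline, post-gameplay and 3-month data, words the hypothesis in terms of engaging with supportED, and calls all these analyses exploratory.

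**How long the session is.** Section 5.7: "Participants will engage with the device for a restricted period of 45 minutes (one-time session"). Section 6.4: "The total session lasting approximately 90 minutes". That section then says that adolescents will be asked to join a questionnaire session and a focus group after the game, without naming an arm.

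**The concern.** An attention/time control is meant to equalise contact, so that a difference between arms can be assigned to what the experimental game contains. Here the arms differ in two ways: the game, and a facilitated group discussion held straight after it. According to Section 5.1 the game deals with warning signs, coping strategies and resources for help. The group discusses that content, and the proximal outcomes include intentions to use a safety plan, coping strategies and knowledge of the same topics. If the arms differ at 3 months, the design cannot say how much came from the game and how much from the discussion, yet Section 7.2 reads as a claim about the game.

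The immediate post-game assessment could isolate the game, but only if it is completed before the group begins. The plan does not expressly fix that order.

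The session length is a separate matter. Staff and schools need one consistent statement of who stays for the group and for how long, and the sections give conflicting ones.

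**Working it through.** **Inputs**

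| Item | Value | Source |
|---|---|---|
| Gameplay, supportED | about 45 min | 4.3, 5.7, 6.4 |
| Gameplay, control | same duration | 6.4 |
| Focus group | 60 min, experimental arm | 4.3, 6.1 |
| Total session | about 90 min | 6.4 |
| Pre-/post-assessments | in the same session, time not stated | 4.3 |

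**1. Can the stated 90 minutes be reproduced?** Not for the supportED arm.

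- Play + group = 45 + 60 = 105 min.
- Excess over the stated session = 105 − 90 = 15 min (15/90 = 17%), with no time allowed for assessments.
- A 60-minute group leaves 90 − 60 = 30 min, less than the game alone.
- Full play leaves 90 − 45 = 45 min for the group and both assessments together, so a 60-minute group cannot fit.
- Reading the 60 minutes as the length of the whole session does not help. It still differs from 90, and leaves 60 − 45 = 15 min for the group and all assessments.

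Assessment time is not given. Assuming 10 to 40 minutes in total, the supportED session is 105 + 10 = 115 to 105 + 40 = 145 min, and the control session 45 + 10 = 55 to 45 + 40 = 85 min. On that assumption, 90 minutes is enough for the control arm only.

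**2. Difference in contact between arms.** Under 4.3 and 6.1, (45 + 60) − 45 = 60 min. This does not depend on assessment time if both arms complete the same assessments.

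**3. What each contrast compares**

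| Time point | supportED arm has had | Control arm has had |
|---|---|---|
| Post-game, questionnaire before group | game | control game |
| Post-game, questionnaire after group | game + group | control game |
| 3 months | game + group | control game |

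Only the first row is a game-only comparison. Section 6.1 puts assessment immediately after play, and 6.4 names the questionnaire before the focus group, but 6.1 and 6.4 also put the group directly after the game. The likely order is clear, but it is not laid down.

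**4. Which outcomes the first row can serve.** They must be measured post-game and able to change within a session. Intentions and knowledge can change in that time, provided they are given then. Items with a past-30-day window (Section 6.8) cannot show a same-day effect of the game. For Brief COPE the documents leave the timing open: 6.8 lists baseline and 3 months, while 6.1, 6.4 and 7.2 describe post-game assessment in general terms.

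**The case against.** The strongest reply is that this is largely labelling. The plan's wording, supportED versus control, names the arms; randomisation is intact; Section 5.1 says the pilot is not powered for efficacy; and Section 7.2 makes every one of these analyses exploratory. That stands as a limit on importance. It does not settle what the contrast estimates, and it leaves in place a stated property of the control that holds for gameplay only.

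A second reply is that the group is data collection. Its stated purpose is to assess usability, acceptability and feasibility, and no section says that it rehearses safety planning. Attendance is also worded as willingness and as a request. This is fair: the documents give no basis for the size of any effect of the group at 3 months, and none is claimed here. The two components still cannot be separated.

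A third reply is that Section 6.4 names no arm, so controls may attend too. Contact could then be equal, but 6.4 would contradict 4.3 and 6.1, so the text needs reconciling on either reading.

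A reader might infer more than the documents support:

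- **That contact differs 2.3-fold (105/45).** This leaves out the assessment time that both arms share. The 60-minute difference is the safer statement.
- **That coping and all suicidal-thoughts measures lack any game-only comparison.** Whether Brief COPE is given post-game is unresolved. The past-30-day heading covers the ASQ; no such window is stated for the CHRT-SR, the named proximal measure of suicidal thoughts.
- **That the randomised comparison is invalid, or the primary objective compromised.** Neither follows.

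**Conclusion.** The concern holds in a limited form. As written, the exploratory 3-month contrast compares supportED plus a post-game focus group with the control game, and a difference cannot be attributed to the game alone. The attention/time-control description is accurate for the gameplay segment only; the planned difference in contact is 60 minutes. This rests on taking 4.3 and 6.1 at their word that only the experimental arm has the group.

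The session-length conflict is definite on the plan's own figures: at least 15 minutes before any assessment. Both 45 and 90 are approximate, but rounding cannot plausibly absorb 15 minutes plus two assessments.

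Severity is minor. The primary usability, acceptability and feasibility outcomes are unaffected.

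**What to change.** (a) In the Synopsis and Sections 5.2, 6.1 and 6.4, limit the attention/time-control claim to the gameplay segment. In 6.1 (item 8) and 7.2, describe the 3-month contrast as supportED plus post-game focus group versus control game.

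(b) State expressly that the post-game questionnaire is completed before the focus group starts. Name the immediate post-game contrast as the game-only comparison for outcomes measured then that can change within a session, such as intentions and knowledge, and note that past-30-day items cannot serve this purpose. Confirm whether Brief COPE is given post-game, since 6.8 reads differently from 6.1, 6.4 and 7.2.

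(c) Reconcile 4.3, 6.1 and 6.4 on which arm attends the group, how long it lasts and the total session time. Record the actual group length in the debrief summary that 7.4 already requires after each session.

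The cost is wording plus one duration field. The arms and the focus group need not change. The downside is a narrower claim at 3 months.
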